1.2. Study Design

This is a randomized, double-blind, placebo-controlled, parallel, multicenter, interventional study to evaluate the efficacy of guselkumab in men and women between the ages of 18 to 75 years, inclusive, with a diagnosis of SSc according to American College of Rheumatology (ACR) and European League Against Rheumatism (EULAR) 2013 criteria with a disease duration of ≤ 36 months (defined as time from first non-Raynaud phenomenon manifestation), and Modified Rodnan Skin Score (mRSS) of ≥ 10 to ≤ 22 units.

Participants will be randomly assigned in a 1:1 ratio, based on randomization strata of presence of interstitial lung disease (ILD [yes, no]), baseline mRSS (low [≥ 10 to ≤ 15] or high [≥ 16 to ≤ 22]), and baseline anti-topoisomerase I antibody status (positive, negative), to 1 of the following treatment groups:

- **Guselkumab (Group/Arm A):** Guselkumab 400 mg IV administration at Weeks 0, 4, and 8 (induction) followed by guselkumab 200 mg subcutaneous (SC) administration every 4 weeks (Q4W) from Week 12 until Week 48 (maintenance)
- **Placebo (Group/Arm B):** Matching placebo IV administration at Weeks 0, 4, and 8 (induction) followed by matching placebo SC administration Q4W from Week 12 until Week 48 (maintenance)

The main study will be conducted in 3 phases: a maximum 6-week screening phase, a 52-week double-blind intervention phase, and a safety follow-up phase with a postintervention follow-up visit at 12 weeks after the participant's last dose of study intervention to collect any adverse events (AEs) since the last study visit. The duration of individual participation will be approximately 66 weeks without LTE.

Participants who complete the main study (Week 0 through 52: ie, after the Week 48 evaluation, prior to Week 52 evaluation) and who, in the opinion of the investigator, may benefit from continued treatment, will participate in the LTE by signing the ICF before or at Week 52. The duration of individual participation will be approximately 66 weeks without LTE and 118 weeks with LTE.

- **Group/Arm A (guselkumab arm from the main study):** Guselkumab 200 mg SC and placebo IV at LTE Weeks 52, 56, and 60 followed by guselkumab 200 mg SC Q4W from LTE Week 64 until Week 100.
- **Group/Arm B (placebo arm from the main study):** Placebo SC and guselkumab 400 mg IV at LTE Weeks 52, 56, and 60 followed by guselkumab 200 mg SC Q4W from LTE Week 64 until Week 100.

[figure not shown]
The objective of LTE is to evaluate the long-term safety and efficacy of guselkumab in SSc patients. The LTE begins with the completion of the assessments at the Week 52, and LTE continues through LTE Week 104. The LTE includes a safety follow-up phase with a postintervention follow-up visit at LTE Week 112 (12 weeks after the participant's last dose of study intervention).

Two planned database locks (DBLs) will occur: EOS of the main study (Week 52 visit for participants who entered LTE or safety follow up visit for participants who did not enter LTE,

hereinafter referred to as “Week 52 DBL”), and EOS of LTE (Week 112 visit, hereinafter referred to as “Final DBL”).

[figure not shown]
A target of 56 participants will be randomly assigned in this study with 28 participants planned per intervention group.

A diagram of the main study design is provided in the following schema.

Abbreviations: DBL=database lock; IV=intravenous; N=number of participants; PE=primary endpoint; R=randomization; SC=subcutaneous; SE=secondary endpoints

A diagram of the LTE period is provided in the following schema.

Abbreviations: DBL=database lock; IV=intravenous; SC=subcutaneous; SE=secondary endpoints

2. STATISTICAL HYPOTHESES

This PoC study aims at detecting an early efficacy signal of guselkumab in participants with SSc, compared to placebo, to support further clinical development.

The primary efficacy endpoint is defined as the change from baseline in mRSS at Week 24.

- The null hypothesis is that the treatment difference between guselkumab and placebo for the primary endpoint is =0.
- The alternative hypothesis is that the treatment difference between guselkumab and placebo for the primary endpoint is $\neq 0$.

Due to the PoC nature of this study, a 2-sided alpha of 0.2 is allocated for testing this hypothesis. The objective will be considered met if the calculated p-value is less than 0.2.

3. SAMPLE SIZE DETERMINATION

There is lack of positive placebo-controlled trials in dcSSc.

Taking into account the following 4 Phase 2/3 placebo-controlled trials (see [Table 2](#)) in SSc with mRSS results reported in the ClinicalTrials.gov registry, a reasonable estimate of the standard deviation (SD) to be used in the sample size calculation of this study has been taken as 8.0.

Table 2: Standard deviations of mRSS in Referenced Phase 2/3 Placebo-controlled Trials in SSc

Trial	Treatment group		Placebo group	
	N	Estimated SD	N	Estimated SD
A Double-Blind, Randomised, Placebo-controlled Trial Evaluating Efficacy and Safety of Oral Nintedanib Treatment for at Least 52 Weeks in Patients With Systemic Sclerosis Associated Interstitial Lung Disease (SSc-ILD) (NCT02597933)	288	4.582	288	4.412
A Phase 3, Multicenter, Randomized, Double-Blind, Placebo-Controlled, Parallel-Group Study to Assess the Efficacy and Safety of Tocilizumab Versus Placebo in Patients With Systemic Sclerosis (NCT02453256)	104	8.169	106	8.142
A Phase 2/3, Multicenter, Randomized, Double-blind, Placebo-controlled Study To Assess The Efficacy And Safety Of Tocilizumab Versus Placebo In Patients With Systemic Sclerosis (NCT01532869)	43	8.266	41	8.933

Trial	Treatment group		Placebo group	
	N	Estimated SD	N	Estimated SD
A Phase 2 Study to Evaluate Subcutaneous Abatacept vs. Placebo in Diffuse Cutaneous Systemic Sclerosis- a Double-blind, Placebo-controlled, Randomized Controlled Trial (NCT02161406)	44	7.562	44	7.562

[Khanna et al \(2006\)](#) revealed that a 95% confidence interval (CI) of [-4.7, -1.7] in mRSS change from baseline to 6 months was considered a clinically meaningful change. The lower bound of this 95% CI, -4.7, has been taken as the expected treatment difference in the sample size calculation of this study, assuming guselkumab can achieve a clinically meaningful change in most of guselkumab-treated participants.

Assuming an SD of 8 points, an 80% power at a 2-sided significance level of 0.20, with a 1:1 randomization ratio, to detect a treatment effect of -4.7 points, a total of at least 54 participants will be required.

Allowing for up to 2 participants randomized but without postbaseline efficacy assessments, approximately 56 (28 each) randomized participants are planned. In order to evaluate the interobserver and intraobserver variability of the mRSS to support Phase 3 planning, it is desirable for each center to randomize 3 participants at least.

4. POPULATIONS (ANALYSIS SETS) FOR ANALYSIS

For purposes of analysis, the following analysis sets are defined:

Table 3: Definition of Analysis Sets

Analysis Sets	Description
Enrolled	All participants who sign the ICF.
Randomized	All participants who were randomized in the study.
Full Analysis Set (FAS)	
All randomized participants who received at least 1 dose (complete or partial) of study intervention.
 
Note: Efficacy and participant information analyses will be based on the randomized intervention groups, regardless of the intervention they actually received.

Full Analysis Set for LTE Period	
All randomized participants who received at least 1 dose (complete or partial) of study intervention during LTE period.

Safety	
All randomized participants who received at least 1 dose (complete or partial) of study intervention.
 
Note: Safety will be analyzed based on the intervention they received, regardless of the intervention groups to which they are assigned.

Safety Analysis Set for LTE Period	
All participants who received at least 1 dose (complete or partial) of study intervention during LTE period.

PK	
All participants who received at least 1 complete administration of guselkumab and have at least 1 observed post dose PK data.

Immunogenicity	
All participants who received at least 1 administration of guselkumab and have at least 1 observed post dose immune response data.

PK/PD Analysis Set for mRSS	
All participants who were randomized to guselkumab and received at least 1 complete administration of guselkumab during main study period, have evaluable data of both PK and PD (mRSS) at the same visit which includes Week 0, and at least one postbaseline timepoint at Week 12, or Week 24 or Week 52 visit.

PK/PD Analysis Set for ACR CRISS	
All participants who were randomized to guselkumab and received at least 1 complete administration of guselkumab during main study period, have evaluable data of both PK and PD (ACR CRISS) at the same visit of at least one postbaseline timepoint at Week 12, or Week 24 or Week 52 visit.

5. STATISTICAL ANALYSES

5.1. General Considerations

Descriptive summary statistics, such as n, mean, standard deviation (SD), median, inter quantile range, minimum, and maximum for continuous variables, and counts and percentages for discrete variables will be used to summarize data as appropriate unless otherwise specified.

5.1.1. Level of Significance

As a PoC study, a 2-sided alpha of 0.2 is allocated for all hypothesis testing throughout the study. As the reference of the internal GO/NO-GO decision making, 95% CIs as well as 80% CIs will be provided for primary endpoint analysis and secondary endpoint analysis.

5.1.2. Missing Data

Unless otherwise specified, a missing-at-random (MAR) missing data mechanism is assumed for all efficacy endpoints and there will be no imputation of missing data prior to the analysis.

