5.3.3. Analysis Methods

The primary analysis will use a Mixed-Effect Model Repeated Measure (MMRM) model. Under the assumption of MAR, the missing data will be accounted for through correlation of repeated measures in the model.

The MMRM model includes treatment group, baseline mRSS, stratification factors (presence of ILD [yes, no] and baseline anti-topoisomerase I antibody status [positive, negative]), visit, treatment group by visit interaction, and baseline mRSS by visit interaction as fixed effects. Stratification factor of baseline mRSS is not included as baseline mRSS is already addressed in the model as a continuous covariate. Treatment effects will be estimated based on least-square means (LSMs) of the differences. The p-values for the LSM differences along with the 2-sided 80% and 95% CIs will be presented. The degree of freedom will be calculated as the error degrees of freedom for the model minus the number of extra random effects estimated.

An unstructured covariance matrix for repeated measures within a participant will be used. In case of lack of convergence, empirical structured covariances will be used in the following order until convergence is reached: 1) Toeplitz 2) first order Autoregressive Moving Average. If the normality assumption is in question, an appropriate transformation will be used.

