5.3.5. Sensitivity Analyses

If at least one data through Week 24 is missing and p-value is <0.2 with the primary analysis, a sensitivity analysis for primary estimand (Composite Estimand) will be performed, using multiple imputation.

Step #1: Utilize a Markov Chain Monte Carlo (MCMC) approach to impute intermediate (nonmonotone) missing data and convert the dataset into a monotone missing data pattern. One hundred monotone datasets will be imputed using the seed 12345, by treatment group.

Step #2: After imputing nonmonotone data, the remaining missing value will be imputed using the PROC MI monotone regression procedure. This approach imputes missing data in a sequential manner, for each time point, a regression model based on all available data at this timepoint (either observed or imputed) is fitted and used to impute values still missing at this timepoint. The ancillary variable included in the model will be treatment group, the stratification factors, and the mRSS scores by visit. The seed is 54321. In this way, one thousand complete datasets are generated.

Step #3: Analyze each of the 100 imputed datasets using the same model specified for the primary analysis and the results will be combined using the PROC MIANALYZE procedure.

The tipping point analysis will be implemented to assess the robustness of conclusions. A constant delta is added or subtracted to the imputed data in the direction of lack of efficacy for guselkumab and in the direction of improvement for placebo. A range of evenly spaced deltas will be used to adjust imputed values in the guselkumab and placebo group independently in order to produce a grid of delta adjustments to missing values in both groups. The size of the deltas will be chosen pragmatically, so that adjustments that lead to p-value ≥ 0.2 are encompassed in the grid. In particular, assuming MAR on placebo, ie, no delta adjustment, an adjustment on the guselkumab arm that just tips the analysis into p-value ≥ 0.2 will be included.

For each pair of delta adjustments, the point estimate of treatment effect, and corresponding p-value combined from results from 1000 adjusted datasets through the PROC MIANALYZE procedures will be presented.

Ukyo and Noma proposed the permutation-based inference methods for the analyses using MMRM that is considered to be more appropriate under small sample settings ([Ukyo 2019](#)). Their method will be applied to examine the robustness of the primary analysis result.

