5.4.2. Secondary Efficacy Endpoints

The secondary efficacy endpoints are:

- Change from baseline in mRSS at Week 52
- The proportion of participants who experience worsening of mRSS at Week 24 and Week 52
- The proportion of participants achieving a score of 0.6 in American College of Rheumatology Combined Response Index in dcSSc (ACR CRISS) at Week 24 and Week 52

- Change from baseline in forced vital capacity (FVC) and percent predicted FVC at Week 24 and Week 52
- Change from baseline in the measured absolute diffusing capacity of the lung for carbon monoxide (DLCO) and the derived percent predicted DLCO at Week 24 and Week 52
- Change from baseline in digital ulcer counts at Week 24 and Week 52
- Change from baseline in Health Assessment Questionnaire-Disability Index (HAQ-DI) score at Week 24 and Week 52

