Change from baseline in digital ulcer counts at Week 24	Difference in LSMs of change from baseline in digital ulcer counts at Week 24 between guselkumab vs placebo
Change from baseline in digital ulcer counts at Week 52	Difference in LSMs of change from baseline in digital ulcer counts at Week 52 between guselkumab vs placebo
Change from baseline in HAQ-DI score at Week 24	Difference in LSMs of change from baseline in HAQ-DI score at Week 24 between guselkumab vs placebo
Change from baseline in HAQ-DI score at Week 52	Difference in LSMs of change from baseline in HAQ-DI score at Week 52 between guselkumab vs placebo

Intercurrent events and their corresponding strategies:

The intercurrent events for all key secondary endpoints at Week 24 are the same as those in the primary estimand, as follows:

1. A prohibited change in SSc medication (for details, see [Appendix 11](#))
2. Discontinuation of study intervention due to lack of efficacy or an AE of Systemic Sclerosis

As rescue medication is available for participants after Week 24, an additional intercurrent event is defined for secondary efficacy endpoints at Week 52.

3. Initiation of rescue medication after Week 24

Intercurrent events 1, 2 and 3 are all handled by the **composite strategy** to assume that the occurrence of intercurrent events indicates an unfavorable outcome. For continuous endpoints, the change from baseline will be zero; and for binary endpoints, the participants are considered as not achieving an improvement (ACR CRISS score ≥ 0.6) or experiencing worsening (an increase from baseline ≥ 5 points and $\geq 20\%$ in mRSS).

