5.4.2.3. Analysis Methods

For continuous endpoint as change from baseline in mRSS at Week 52, an MMRM model with treatment group, baseline mRSS, stratification factors (presence of ILD [yes, no] and baseline anti-topoisomerase I antibody status [positive, negative]), visit, treatment group by visit interaction, and baseline mRSS by visit interaction as fixed effects will be applied. The estimates of the treatment difference between guselkumab and placebo will be provided by the difference in the least squares means (LSMs), as well as the 2-sided 80% and 95% CIs for the differences and p-values.

For continuous endpoints other than change from baseline in mRSS at Week 52, an MMRM model with treatment group, baseline value of the endpoint, stratification factors (presence of ILD [yes, no], baseline mRSS (low [≥ 10 to ≤ 15], high [≥ 16 to ≤ 22]) and baseline anti-topoisomerase I antibody status [positive, negative]), visit, treatment group by visit interaction, and baseline value of the endpoint by visit interaction as fixed effects will be applied. The estimates of the treatment difference between guselkumab and placebo will be provided by the difference in the least squares means (LSMs), as well as the 2-sided 80% and 95% CIs for the differences and p-values. The degree of freedom will be calculated as the error degrees of freedom for the model minus the number of extra random effects estimated.

An unstructured covariance matrix for repeated measures within a participant will be used. In case of lack of convergence, empirical structured covariances will be used in the following order until convergence is reached: 1) Toeplitz 2) first order Autoregressive Moving Average. If the normality assumption is in question, an appropriate transformation will be used.

For binary endpoints such as proportion of participants achieving an ACR CRISS score of 0.6, a logistic regression model that includes factors for treatment group and stratification factors (presence of ILD [yes, no], baseline mRSS (low [≥ 10 to ≤ 15] or high [≥ 16 to ≤ 22]) and baseline anti-topoisomerase I antibody status [positive, negative]) will be applied provide the odds ratios, p-values, as well as the 2-sided 80% and 95% CIs for comparisons between guselkumab and placebo.

5.4.2.4. Supplementary Analysis for Change from Baseline in MRSS at Week 52

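### mRSS-worsening and ACR CRISS responder analyses assume MAR, but a single-visit logistic model without imputation needs a stronger assumption for outcomes missing outside the listed intercurrent events

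*SAP*

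**What the plan says.** - **Missing data (SAP 5.1.2).** The default, open to stated exceptions, reads: "a missing-at-random (MAR) missing data mechanism is assumed for all efficacy endpoints and there will be no imputation of missing data prior to the analysis".
- **Primary endpoint (SAP 5.3.3).** Under MAR, "the missing data will be accounted for through correlation of repeated measures in the model".
- **Binary secondary endpoints (SAP 5.4.2).** One is "The proportion of participants who experience worsening of mRSS at Week 24 and Week 52". ACR CRISS of at least 0.6 is assessed at the same two visits.
- **Binary model (SAP 5.4.2.3).** The method is "a logistic regression model that includes factors for treatment group and stratification factors". It has no visit term and no earlier post-baseline score, and the section gives no rule for a missing outcome.
- **Composite rule (SAP 5.4.2.2).** After an intercurrent event, "for binary endpoints, the participants are considered as not achieving an improvement" or as having worsened. The events are a prohibited change in SSc medication, "Discontinuation of study intervention due to lack of efficacy or an AE of Systemic Sclerosis" and, for Week 52, rescue medication started after Week 24.
- **Multiple imputation (SAP 5.3.5).** If some data through Week 24 are missing and the primary p-value is below 0.2, "a sensitivity analysis for primary estimand (Composite Estimand) will be performed, using multiple imputation". It is planned for nothing else.

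**The concern.** MAR allows the chance of a missing Week 24 or Week 52 score to depend on mRSS already observed. The MMRM uses that history. A logistic model at one visit does not: with no imputation, participants without the outcome leave the analysis. The result is then valid in general only if missingness depends on nothing beyond treatment and strata, which is a stronger assumption than the one SAP 5.1.2 declares. Two results from the same skin scores, the mean change and the proportion worsening, would rest on different missing-data assumptions.

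The composite rule covers only the listed events. Withdrawal of consent, loss to follow-up, missed visits, and missing data after stopping for some other adverse event are outside it. SAP 5.1.4 analyses by nominal visit and has no rule mapping an early-termination mRSS to Week 24 or 52. A participant clearly worse at Week 20 who then withdraws consent would therefore not be counted.

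These endpoints carry nominal p-values (SAP 5.4.1). However, SAP 5.1.1 makes the 80% and 95% confidence intervals for secondary endpoints a reference for the internal go/no-go decision, so the estimates will be used.

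**Working it through.** **1. The plan's own figure.** Inputs from SAP 3: difference 4.7, SD 8, two-sided alpha 0.20, power 80%, 1:1 allocation.

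n per arm = 2(1.2816 + 0.8416)² × 8² / 4.7² = 2 × 4.508 × 64 / 22.09 = 26.1, so 27 per arm and 54 in total. This matches the SAP. The allowance of 2 in 56 is for participants with no post-baseline efficacy assessment at all. No rate is given for missing Week 24 or Week 52 outcomes, and no sample size for the binary endpoints.

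**2. Does complete-case analysis fail under MAR?** The check was a large-sample simulation with 300,000 participants per arm. From the documents: SD of change 8 and difference -4.7 at Week 24, six 4-weekly visits, and worsening defined as a rise of at least 5 points and at least 20%. Assumed:
- baseline mRSS about 16 (SD 3.5, kept within 10 to 22);
- correlation 0.8 between adjacent visits;
- mean placebo change of -1 at Week 24;
- missingness that remains after the composite rule has been applied;
- where missingness depends on mRSS, 0.2 log-odds per point of Week 12 change.

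Both arms have the same overall missing rate; the scenarios differ in which arm's missingness depends on mRSS. Odds ratios are unadjusted for strata. True worsening is about 24.6% on placebo and 10.1% on guselkumab.

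| Missing | Depends on mRSS in | True OR | Complete-case OR | OR weighted by earlier mRSS |
|---|---|---|---|---|
| 5% | neither arm | 0.344 | 0.344 | 0.344 |
| 5% | both arms | 0.352 | 0.347 | 0.353 |
| 5% | placebo only | 0.346 | 0.364 | 0.346 |
| 5% | guselkumab only | 0.345 | 0.322 | 0.345 |
| 25% | neither arm | 0.346 | 0.346 | 0.346 |
| 25% | both arms | 0.344 | 0.322 | 0.344 |
| 25% | placebo only | 0.347 | 0.437 | 0.346 |
| 25% | guselkumab only | 0.343 | 0.253 | 0.341 |

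For the 25%, placebo-only row, the complete-case rates are 20.5% and 10.2%: (0.102/0.898) / (0.205/0.795) = 0.44. With dependence in both arms, the rates fall to 23.6% and 9.7% at 5% missing, and to 20.6% and 7.7% at 25%. Using the earlier mRSS removes the bias in every row.

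**3. Effect of the composite rule.** A second simulation (200,000 per arm) gave worsened participants a 10% or 20% withdrawal risk per visit and others 2%, alike in both arms. It varied the share of worsened leavers whose exit is a listed event. That share is an assumption.

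| Share listed | Risk | Placebo, complete-case v true |
|---|---|---|
| 50% | 10% | 28.5% v 28.9% |
| 50% | 20% | 29.9% v 30.8% |
| 80% | 10% | 30.8% v 30.3% |
| 80% | 20% | 34.1% v 33.5% |

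At a 50% share, guselkumab read 13.1% v 13.2% and 14.7% v 14.9%. With no listed events, placebo read 22.2% to 24.4% against a true 26.5% to 26.7%.

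**4. Planned trial size.** At 28 per arm, with assumed dropout rates, no listed events and unequal dropout, the complete-case odds ratio was 0.27 to 0.45 against a true 0.35 to 0.36. Imputing Week 24 mRSS within arm gave 0.36.

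**5. Sampling error for comparison.** With 28 per arm and rates of 24.6% and 10.1%, SE(log OR) = √(1/6.89 + 1/21.11 + 1/2.83 + 1/25.17) = 0.77. Around an odds ratio of 0.344, the 80% interval is exp(-1.066 ± 1.2816 × 0.765), or 0.13 to 0.92.

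**The case against.** The strongest reply is that the composite rule already classifies many of the participants who worsen and leave. Step 3 bears this out: with half or more of those exits listed, the placebo bias is under one point or reverses. The estimand's summary is the odds ratio, which hardly moves when dropout works alike in both arms. Even the extremes in step 2 lie well inside the interval in step 5. The larger shifts need substantial residual missingness tied to mRSS in one arm only, and the documents do not say this will happen. All of this stands, and it limits the importance of the point.

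A second reply is that SAP 5.1.2 itself rules out imputation and the protocol (9.4.3) prescribes a logistic model. A reader might infer that the MAR statement commits the sponsor to multiple imputation; it does not, because the same sentence excludes imputation before analysis. What remains is that the declared assumption does not justify the chosen method, and no rule covers the residual missing outcomes. Deletion of incomplete cases is implied by SAP 5.4.2.3, not written there; only the exploratory section (SAP 5.5.2) says outright that observed data are used.

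A reader might also infer that suitable imputed data will exist already. They may not: SAP 5.3.5 runs only if the primary p-value is below 0.2, stops at Week 24 and covers mRSS alone. Extending its within-arm step to Week 52 with all ACR CRISS components would involve 14 mRSS values, 5 each of HAQ-DI, patient global and physician global, and 4 FVC values: 14 + 15 + 4 = 33 variables for about 28 participants per arm. That is not workable as it stands.

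**Conclusion.** The point holds as a limited inconsistency. For binary outcomes missing outside the listed intercurrent events, the planned analysis needs a stronger assumption than the MAR assumption in SAP 5.1.2, and it ignores mRSS collected every 4 weeks. The proportions can be biased, and the odds ratio too if missingness depends on mRSS differently by arm. Under the assumptions in the working, the odds ratio ranges from 0.32 to 0.36 at 5% residual missingness and from 0.25 to 0.44 at 25%, against about 0.35. There is no bias if missingness is unrelated to mRSS.

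A reader might infer that the reported worsening proportions will be too low. The documents do not support a fixed direction: the residual missing rate is not given, and the sign changes with the share of exits the composite rule captures. Nor does the point touch the proof-of-concept test, which rests on the MMRM. It is a desirable correction to secondary analyses.

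**What to change.** **mRSS worsening.** Impute mRSS by visit under MAR with the SAP 5.3.5 approach, run whatever the primary p-value. For Week 52 use a reduced model, for example both arms pooled with a treatment term and a limited set of prior visits. Then apply the composite rule, dichotomise, fit the planned logistic model in each dataset and combine by Rubin's rules. Keep the complete-case result as a sensitivity analysis. Before reuse, settle the number of datasets in 5.3.5, which generates 1000 in one step and analyses 100 in the next.

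**ACR CRISS.** Full imputation of the components should not be required. Keep Step 1 events and intercurrent events as non-improved, report the observed-data result, and state in SAP 5.4.2.3 that it assumes missingness depends only on treatment and strata.

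**Cost.** SAP wording and modest extra programming before the Week 52 database lock. No change to data collection or to the primary analysis.
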